302 using Rubin's rules. This approach is appropriate for data sets that have a monotone missing

303 data pattern. If the data set does not precisely have this pattern, the monotone data augmentation
304 method using Markov-Chain Monte-Carlo as proposed by Li (1988) and Liu (1993) will be used
305 to impute the small amount of missing data that is required to make the missing data pattern
306 monotone before applying the multiple imputation algorithm described above. This approach
307 should accommodate missing data in an appropriate way under the missing at random (MAR)
308 assumption.

309

310 **3.2.7 Sensitivity Analysis**

311 The primary analysis will be completed using the ITT principle described in *Section 3.1*. The
312 primary analysis will be repeated with the following considerations as a secondary analysis:

- 313 • According to treatment received (whether or not this was the randomly assigned
314 treatment)
- 315 • Excluding participants without outcome PMD (Month 6 or exam at early treatment
316 failure)
- 317 • Exclude participants who took less than 80% of tolerated dosage of medication
- 318 • Exclude participants with major protocol violations such as: receipt of additional
319 treatment outside of treatment assignment prior to first of 6-month visit or visit at which
320 treatment failure declared, or major eligibility deviation that could impact the ability to
321 assess the primary outcome.

322 The identification of subjects to be excluded from these analyses will be determined before the
323 masking is broken (i.e., before data analysis).

324

325

326 **3.3 Analysis of Secondary Outcome Variables for Efficacy**

327 **3.3.1 Definition of Secondary Outcomes**

328 The following are secondary outcomes for efficacy:

- 329 • Change from baseline PMD to Month 6 PMD
 - 330 ○ PMD defined as described in *Section 3.2.1*
 - 331 ○ Month 6 PMD value will be used even for participants with treatment failure prior
332 to Month 6
- 333 • Change from baseline to Month 6 CSF opening pressure measurement by lumbar
334 puncture
- 335 • Change from baseline to Month 6 in papilledema grade
 - 336 ○ Papilledema grade determined by reading center and grade determined by study
337 center will be considered separate outcomes and will be analyzed separately
- 338 • Change from baseline to Month 6 (pre-lumbar puncture) in RNFL thickness
- 339 • Change from baseline to Month 6 (pre-lumbar puncture) in total retinal thickness
- 340 • Change from baseline to Month 6 (pre-lumbar puncture) in optic nerve head volume
- 341 • Change from baseline to Month 6 (pre-lumbar puncture) in ganglion cell layer thickness

- 342 • Change from baseline to Month 6 (pre-lumbar puncture) in optic nerve canal shape
- 343 • Change from baseline to Month 6 in ETDRS visual acuity score
- 344 • Change from baseline to Month 6 in SF-36v2 scores
 - 345 ○ Change will be calculated separately for each of the eight health domains and the
 - 346 physical component summary (PCS) and mental component summary (MCS)
 - 347 scores
 - 348 ○ Scores determined via SF-36v2 scoring software
- 349 • Change from baseline to Month 6 in VFQ-25 score
 - 350 ○ Score determined as an average of sub-scale scores as described in the VFQ-25
 - 351 manual ([..\References\Participant Questionnaires\VFQ25_Manual.pdf](#))
 - 352 ▪ Scoring of missing items will follow the scoring instrument
- 353 • Change from baseline to Month 6 in VFQ-25 Neuro-Ophthalmic Supplement score
 - 354 ○ Score determined as described in the 10-item Neuro-Ophthalmic instructions
 - 355 ([..\References\Participant Questionnaires\Prior to Executed](#)
 - 356 [Agreement\10ItemNeuroOphthalVFQ25.pdf](#))
 - 357 ▪ Scoring of missing items will follow the scoring instrument
- 358 • Change from baseline to Month 6 in HIT-6
 - 359 ○ Score determined as a sum of scores for each question (Never = 6, Rarely = 8,
 - 360 Sometimes = 10, Very Often = 11, Always = 13; total score range 36 to 78 with
 - 361 higher score indicating greater life impact)
 - 362 ○ Surveys with ≥ 1 missing responses will be given an overall null score for the visit
- 363 • Change in headache severity from baseline to Month 6 as reported on the Headache
- 364 Assessment form
 - 365 ○ Analyzed as a continuous value with the following categories assigned for
 - 366 display:
 - 367 ▪ Mild = score 1-4 | Moderate = score 5-7 | Severe = score 8-10
- 368 • Month 6 VFRC determination of whether the visual field examination has improved,
- 369 remained the same, or worsened
 - 370 ○ All available visual field examinations will be analyzed. For the initial secondary
 - 371 outcome, the Month 6 VFRC rating will be used; a supplemental secondary
 - 372 outcome will use the VFRC rating at time of treatment failure for subjects
 - 373 experiencing treatment failure prior to Month 6.
- 374 • Change in weight from baseline to Month 6

375
 376 Data from all eligible eyes will be included in the analysis. With the exception of CSF opening
 377 pressure and VFRC determination of visual field status, the outcomes also will be examined with
 378 change from baseline to Months 12, 24, 36.

379
 380 **3.3.2 Secondary Statistical Models**

381 Treatment effect on secondary outcome variables for efficacy that are continuous will be
382 analyzed using the same methods described in *Section 3.2.2* for the primary outcome variable,
383 except that a working correlation structure will not be needed for variables that are not eye-
384 specific. Variables to be analyzed in this manner are:

- 385 • Change in PMD at Month 6
- 386 • Change in CSF opening pressure (does not require working correlation structure)
- 387 • Change in papilledema grade (both reading center and study center outcomes)
- 388 • Change in RNFL thickness
- 389 • Change in total retinal thickness
- 390 • Change in optic nerve head volume
- 391 • Change in ganglion cell layer thickness
- 392 • Change in optic nerve canal shape
- 393 • Change in ETDRS visual acuity score
- 394 • Change in SF-36 scores (8 subscale domains, PCS and MCS; does not require working
395 correlation structure)
- 396 • Change in VFQ-25 score (does not require working correlation structure)
- 397 • Change in VFQ-25 Neuro-Ophthalmic Supplement score (does not require working
398 correlation structure)
- 399 • Change in HIT-6 (does not require working correlation structure)
- 400 • Change in headache severity as reported on Headache Assessment form (does not require
401 working correlation structure)
- 402 • Change in weight

403
404 The treatment effect on the ordinal outcome of Month 6 visual field examination status by
405 the VFRC (improved, no change, worse) will be assessed via a logistic regression model
406 (proportional odds model). A likelihood ratio test will be performed for significance of the
407 adjusted treatment group odds ratios representing pair-wise treatment group comparisons;
408 98.3% confidence intervals will be constructed for these odds ratios.

409
410 All models will include treatment group as the factor of interest and the baseline value of the
411 outcome variable as a covariate (to replace baseline PMD adjustment in the primary for
412 continuous outcomes; Month 6 visual field examination status by VFRC will retain inclusion
413 of baseline PMD).

415 **3.3.3 Adjustment for Baseline Covariates**

416 Assessment for and implementation of adjustment for baseline covariates will follow methods
417 described in *Section 3.2.3*.

419 **3.3.4 Investigation of Treatment by Covariate Interactions**

420 Investigation of interaction between treatment group and selected baseline covariates will follow
421 methods described in *Section 3.2.4*.

422

423 **3.3.5 Verification of Model Assumptions**

424 Methods described in *Section 3.2.5* will be used to check underlying assumptions of the
425 statistical model for each outcome.

426

427 **3.3.6 Treatment of Missing Data**

428 Methods described in *Section 3.2.6* will be used to impute missing data at Month 6 for
429 continuous outcomes.

430

431 Missing values of Month 6 visual field examination status will not be imputed.

432

433 **3.4 Compliance Outcomes**

434 Data concerning compliance with acetazolamide (pill counts, serum bicarbonate levels) and
435 surgical therapy will be summarized by treatment group and visit. Subjects with two eligible
436 eyes will have this information summarized by eye as well as by treatment group and visit.

437

438 **3.5 Analysis of Safety and Tolerability Outcomes**

439 **3.5.1 Adverse Events**

440 All reportable adverse events will be tabulated by treatment group in a listing of each reported
441 Medical Dictionary for Regulatory Activities (MedDRA) term and summarized over each
442 MedDRA System Organ Class. Details will be provided in a listing of each event.

443 In addition, the following will be tabulated by treatment group. When applicable, events will be
444 tabulated by eye within person:

- 445 • Number of adverse events per subject
- 446 • Number of subjects with at least one event
- 447 • Number of subjects with at least one event per person-month (person-month based on
448 subject duration in the study)
- 449 • Number of serious adverse events per subject
- 450 • Number of subjects with at least one serious adverse event
- 451 • Number of hospitalizations and reasons for the hospitalization (overall and per subject,
452 separately)
- 453 • Number of adverse events thought by investigator to be related to study drug and
454 frequency of each type of such event
- 455 • Number of subjects who stopped the intervention in response to an adverse event

456 For binary variables (occurrence of at least one event, occurrence of at least one serious adverse
457 event, occurrence of at least one hospitalization, occurrence of at least one adverse event related
458 to treatment, occurrence of stopping the intervention in response to adverse event), Fisher exact
459 tests will be used to compare treatment groups. For counts (number of adverse events per
460 subject, number of serious adverse events per subject, number of hospitalizations per subject),
461 groups will be compared using Poisson regression with inclusion of the logarithm of study
462 follow-up duration for the participant as an offset term; a negative binomial model will be
463 considered if overdispersion is present, and a zero-inflated negative binomial model will be used
464 if there appear to be excessive zero counts.

465 For each adverse event, the treatment groups will be compared in a pair-wise fashion regarding
466 the occurrence of at least one event using Fisher's exact tests; numbers of individual events will
467 also be described. The comparisons will be repeated excluding all mild symptoms. Similar
468 analyses will be performed after grouping adverse events by body system using Medical
469 Dictionary for Regulatory Activities (MedDRA) coding. All subjects will be included in these
470 analyses.

471

472 **3.5.2 Laboratory Test Results and Vital Signs**

473 Continuous measures of safety such as laboratory test results (CBC with platelet count,
474 electrolytes, potassium, bicarbonate, and liver function tests) and vital signs and anthropometric
475 measures (blood pressure, weight, and waist circumference) will be analyzed descriptively
476 through summary statistics and tabulations.

477 Proportions of subjects with particular laboratory test abnormalities will be compared between
478 the treatment groups in a pair-wise fashion using Fisher's exact tests.

479

480 **3.6 Analysis of Long-Term Follow-Up Data**

481 The following outcome will be examined in analysis of long-term follow-up data:

- 482 • Time from randomization to treatment failure

483

484 **3.6.1 Analysis Model**

485 Treatment group differences with respect to long-term outcomes will be assessed by fitting a Cox
486 proportional hazards regression model with treatment group as the factor of interest and baseline
487 PMD in the best eligible eye as a covariate. Due to the discrete time data, Efron approximation
488 will be used to deal with tied event times. The model will be used to determine Bonferroni-
489 adjusted 98.3% confidence intervals for the adjusted hazard ratios for the three pair-wise
490 treatment group comparisons. Likewise, likelihood ratio tests will be performed for the
491 significance of these hazard ratios using a Bonferroni-adjusted two-tailed significance level of
492 1.7%. Kaplan-Meier curves will be used to describe the cumulative probability of treatment
493 failure over time in each treatment group.

494
495 For subjects who do not experience the outcome, event times will be censored at the last subject
496 contact at which the subject was determined to not have experienced the outcome (e.g., at time of
497 premature withdrawal from the trial or at the final trial visit).
498

499

500 **3.6.2 Adjustment for Baseline Covariates**

501 Adjustment for additional baseline covariates (in addition to baseline PMD and papilledema
502 grade in best eligible eye) may be considered depending on the comparability of the treatment
503 groups at baseline (refer to *Section 3.2.3*).
504

504

505 **3.6.3 Investigation of Treatment by Covariate Interactions**

506 Examination of interactions between treatment group and selected baseline covariates will be
507 performed using the Cox proportional hazards model following the guidelines established in
508 *Section 3.2.4*.
509

509

510 **3.6.4 Verification of Model Assumptions**

511 The underlying assumptions of the Cox proportional hazards model will be checked and a
512 thorough analysis of the martingale residuals and other diagnostics will be performed. Remedial
513 measures (covariate transformation) will be taken if serious violations of these assumptions are
514 detected.
515

515

516 The proportional hazards assumption will be assessed graphically by plotting $\log(-\log(\hat{S}(t)))$ vs.
517 $\log(\text{time})$ for each of the treatment groups, and by examining plots of smoothed Schoenfeld
518 residuals. The assumption also will be examined by dividing the time scale into 6-month periods
519 and estimating the treatment group hazard ratios separately in each of these periods through the
520 use of time-dependent covariates. The period length of 6 months may be adjusted prior to
521 unmasking, based on the observed distribution of event times, if relatively few events occur
522 during 6-month periods. Treatment group comparisons will be described in this manner if the
523 proportional hazards assumption appears to be seriously violated.
524

524

525 The assumption of independence between censoring time and the (unobserved) event time will
526 be assessed by performing a sensitivity analysis in which subjects with event times that are
527 censored prior to their scheduled end of follow-up will be treated as having experienced the
528 event a short time (one week) after censoring.
529

529

530 **3.7 Interim Analysis**

531 **3.7.1 Interim Analysis for Safety**

532 Interim analyses of safety data will be performed periodically throughout the trial. While the
533 safety of subjects will be the primary concern of the DSMC, it is difficult to formulate precise

534 stopping guidelines that would cover all of the possible situations that might arise. Adverse
535 events, particularly serious adverse events and surgical complications, will have to be considered
536 carefully by the DSMC in terms of treatment group imbalances and severity. Events of particular
537 concern include the following: death, absence of light perception, hypokalemia (from Lasix use),
538 surgery-associated visual loss (from either VPS or ONSF), fenestration failure and orbital
539 infection (from ONSF), and shunt failure, infection, seizures, and subdural hematoma (from
540 VPS). If potential safety concerns are identified, the DSMC may require review of visual field
541 data in order to evaluate the risk-benefit of continuing the trial as planned or modifying (or
542 halting) the trial.

543

544 **3.7.2 Interim Analysis for Efficacy**

545 We will perform a single interim analysis for efficacy based on the primary outcome efficacy
546 variable. This will be performed after ~50% of the subjects have completed (or were scheduled
547 to have completed, based on their randomization date) their Month 6 visit and will only include
548 data from these subjects. Given that recruitment of the 180 subjects will take place over 3 years,
549 assuming that recruitment is uniform over time, it is anticipated that slightly fewer than 70% of
550 the subjects will be enrolled at the time of the interim analysis.

551 The analysis will involve pair-wise comparisons among the treatment groups with respect to the
552 primary outcome efficacy variable; the significance level used for each comparison will be
553 determined by an O'Brien-Fleming α -spending function for a two-group comparison divided by
554 3 (Bonferroni correction). In this case, the boundaries will be $Z = 3.394$ for the interim analysis
555 and $Z = 2.400$ for the final analysis. Assuming that there are 30 subjects per group and that the
556 standard deviation is 6.5 dB at the interim analysis, the boundary will be crossed if a group
557 difference exceeds approximately 5.7 dB. This monitoring procedure will have a negligible
558 impact on the overall Type I error probability: the significance level at the final analysis
559 corresponding to $Z = 2.400$ is $\alpha = 0.0164$. Point and interval estimates of treatment effects for the
560 primary analysis, as well as reported p-values, will be adjusted for the interim analysis. The bias-
561 adjusted mean will be used for point estimation and confidence intervals and p-values based on
562 the MLE (sample mean) ordering of the sample space defined by the group sequential design
563 will be reported.

564 The efficacy boundary will be considered to be non-binding. We believe that it may be prudent
565 to halt or modify the trial only if (1) two of the treatment groups are each shown to be superior to
566 the third (in which case the third group may be dropped) or (2) one of the treatment groups is
567 shown to be superior to each of the other two (in which case the trial may be halted). Of course,
568 the relative safety profiles of the treatments would have to factor into these considerations as
569 well.

570

571

572 **3.8 Additional Tabulations**

573 A flow chart will track all participants who were enrolled, indicating the reason for any who did
574 not complete the study and providing details on randomized subjects determined to be ineligible.
575 A summary of safety visits, phone calls, and information on completion of questionnaires will be
576 compiled.

577
578 Tabulations will include:

- 579 • Demographic and clinical characteristics at enrollment by treatment group
- 580 • Eligible eye characteristics by treatment group
- 581 • Non-eligible eye characteristics by treatment group
- 582 • Overall number of treatment failures by treatment group
- 583 • Overall number of surgical malfunctions by treatment group (ONSF and VPS groups)
- 584 • Duration (days) from enrollment to randomization
- 585 • Duration (days) from randomization to surgery (ONSF and VPS groups)

586
587 **Specific Protocol Tabulations by Treatment Group**

588 6-Month RCT

- 589 • Receipt of surgery other than that randomly assigned
- 590 • Adherence to medical management and diet by visit
- 591 • Daily dosage of acetazolamide and furosemide prescribed at each visit
- 592 • Medical therapy at each visit
- 593 • ONSF completion status (ONSF group)
- 594 • VPS completion status (VPS group)
- 595 • Surgical complications (separately for ONSF and VPS groups)
- 596 • Reoperations (ONSF)
- 597 • Shunt revisions (VPS)
- 598 • Headache by visit
- 599 • Weight by visit
- 600 • Visual field at follow-up (eligible eyes and non-eligible eyes, separately)
- 601 • Visual acuity at follow-up (eligible eyes and non-eligible eyes, separately)
- 602 • Papilledema grading at follow-up (eligible eyes and non-eligible eyes, separately)
- 603 • RNFL and macula GCL at follow-up (eligible eyes and non-eligible eyes, separately)
- 604 • Protocol deviations

605
606 Treatment Failure Identification Phase (Post 6-Month RCT)

- 607 • Adherence to medical management and diet by visit
- 608 • Daily dosage of acetazolamide and furosemide prescribed at each visit
- 609 • Medical therapy at each visit
- 610 • Protocol deviations.

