One eligible eye and non-eligible eye too good	One eye that was eligible at baseline, regardless of what happened to either eye during study
One eligible eye and non-eligible eye too bad	One eye that was eligible at baseline, regardless of what happened to either eye during study
Two eligible eyes	Both eyes that were eligible at baseline, regardless of what happened to either eye during study

216
 217
 218 Treatment of subjects who have reached criteria for treatment failure will be at the discretion of
 219 the Site Investigator, and this treatment may yield a different outcome than randomized
 220 treatment. For this reason, the primary outcome variable for subjects who reach criteria for
 221 treatment failure prior to Month 6 will be the PMD measured at the time of treatment failure for
 222 purposes of the primary analysis. It is anticipated that no more than 15% of subjects will reach
 223 criteria for treatment failure prior to Month 6.
 224

225 PMD (baseline or outcome) will be the average PMD from the two reliable visual field
226 examinations (i.e. meeting Visual Field Reading Center criteria) performed at the visit; if only
227 one reliable result is obtained on the visual field examination, the one reliable result will be
228 analyzed; if a reliable result is not obtained on the visual field examinations, the PMD will be
229 considered missing.

230

231 Outcome PMD (excluding PMD at time of treatment failure) from visual field testing performed
232 out of the window of 168-242 days from randomization will be considered missing for the
233 primary analysis. Note this means a subject can be up to two weeks early and up to a full 60
234 days late, this latter choice was made with clinician input that they would rather have a
235 measurement than impute.

236

237 **3.2.2 Primary Statistical Model**

238 The primary statistical analysis will involve fitting an analysis of covariance model using
239 generalized estimating equations (GEE) with treatment group as the factor of interest and
240 baseline PMD as a covariate. These analyses will accommodate correlation among the within-
241 subject responses between the two eyes; an exchangeable working correlation structure will be
242 used. Standard errors for the model parameters will be estimated using the robust “sandwich”
243 estimators. The model also does not rely on the assumption of normality.

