244 This model will be used to determine Bonferroni-adjusted confidence intervals for the three pair-
245 wise differences among the adjusted treatment group mean responses (treatment effects);
246 likewise, tests will be performed to compare the adjusted treatment group means using a
247 Bonferroni-adjusted two-tailed significance level. An overall confidence coefficient of 98.3%
248 and corresponding significance level of 1.7% for each comparison will be maintained, but as
249 discussed in section 3.7.2 below, the confidence coefficient for interval estimation and
250 significance level for hypothesis testing will be adjusted for the interim analysis for efficacy.

251

252 **3.2.3 Adjustment for Baseline Characteristics**

253 Baseline characteristics of subjects will be summarized overall and by treatment group. Formal
254 statistical comparisons between treatment groups will not be performed; instead, potential
255 confounding will be explored by examination of the magnitudes of treatment group differences
256 in the distributions of visual acuity, papilledema grade, and duration of IIH. Other variables for
257 which there are baseline differences among treatment groups that could be associated with the
258 outcome also will be evaluated for a potential confounding effect. Continuous variables will be
259 described using means, standard deviations, medians, quartiles, and ranges, and categorical
260 variables will be described using percentages.

261 If clinically important differences are found between the groups at baseline, the primary outcome
262 analyses will be repeated after statistically adjusting for these differences. These analyses will be
263 considered secondary, however.

264

265 **3.2.4 Investigation of Treatment by Covariate Interactions**

266 We will investigate the interaction between treatment group and selected baseline covariates
267 (age, race/ethnicity, PMD (average of measures from two reliable visual field examinations),
268 papilledema grade, RNFL thickness, total retinal thickness, optic nerve head volume, visual
269 acuity, presence of transient visual obscurations, and the symptom of constant visual loss)
270 separately by adding the appropriate main effect and interaction terms to the primary statistical
271 model and testing for significance of the interaction.

272 Since the power to detect potentially meaningful interactions will be limited, the magnitudes of

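### Sandwich standard errors with no small-sample correction, judged against normal cut-offs, put the final test near 2.0% instead of 1.64% per comparison and the interim test at roughly 2 to 2.6 times its nominal level

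*SAP*

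**What the plan says.** SAP 3.2.2 (and Protocol 9.3.1) fits an analysis of covariance by GEE, with treatment group and baseline PMD as terms. Each subject is a cluster of one or two eyes, and "an exchangeable working correlation structure will be" used. On variance estimation it says "Standard errors for the model parameters will be estimated using the robust" sandwich estimators. On the error rate it says "and corresponding significance level of 1.7% for each comparison will be maintained", subject to adjustment for the interim look.

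SAP 3.7.2 (and Protocol 9.8.2) sets the cut-offs on the normal scale. The text reads "Bonferroni correction). In this case, the boundaries will be" Z = 3.394 at the interim and Z = 2.400 at the final analysis, and the latter is equated to a level of 0.0164. The interim is planned on 30 subjects per group with a standard deviation of 6.5 dB, so that a crossing occurs if a group "difference exceeds approximately 5.7 dB".

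Neither document names a small-sample correction to the sandwich or a t reference. The missing-data section (SAP 3.2.6) pools by Rubin's rules and adds no such correction either.

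**The concern.** The sandwich estimator builds its variance from fitted residuals, which are on average smaller than the true errors, so with few clusters the standard error is too small. It is also a noisy estimate, and referring the ratio to a normal instead of a t distribution ignores that noise. Both errors push towards rejection, and both grow further out in the tail, where 3.394 lies. The SAP's remark that the model does not need normality is a large-sample property and does not cover this.

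At stake is the level of the primary test for all three pairwise comparisons, and the coverage of their intervals. SAP 3.3.2 carries the same method to the continuous eye-specific secondary outcomes. Leaving the estimator unnamed also leaves the choice open until results can be seen.

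**Working it through.** **Step 1: the plan's own figures reproduce.**
- Final level: 2 × (1 − Φ(2.400)) = 0.0164, as stated.
- Interim level: 2 × (1 − Φ(3.394)) = 0.00069, rounded to 0.0007.
- Both looks together, with correlation √0.5 between them: 0.01667 per comparison, which is 0.05/3.
- Interim difference at the boundary: 3.394 × 6.5 × √(2/30) = 5.70 dB, as stated.

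The boundary arithmetic is therefore correct for a statistic that is exactly normal. The question is whether the planned statistic is close enough to that.

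**Step 2: the reference distribution alone.** The model has four mean parameters (three groups and one slope). With 90 subjects at the interim there are 86 degrees of freedom, and P(|t| > 3.394) = 0.00104, about 1.5 times 0.00069. With 162 subjects at the end (3 × 54) there are 158, and P(|t| > 2.400) = 0.0176 against 0.0164. The downward bias of the sandwich comes on top of this.

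**Step 3: simulation of the planned test under the null.**

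Inputs from the documents:
- SD 6.5 dB, about 40% of subjects with two eligible eyes, between-eye correlation 0.82 (SAP 2.0)
- 54 evaluable of 60 per group at the end (SAP 2.0)
- 30 per group at the interim (SAP 3.7.2), or 27 if the same 10% loss is applied (30 × 0.9)

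Assumed, because the documents do not give them:
- baseline PMD uniform from −27 to −6 dB
- between-eye correlation of baseline 0.8 (0.3 also run)
- slope of change on baseline −0.5
- no missing data

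Each simulated trial was fitted by GEE with exchangeable correlation. The variance was A⁻¹(Σ UᵢUᵢᵀ)A⁻¹, where A = Σ XᵢᵀVᵢ⁻¹Xᵢ, Uᵢ = XᵢᵀVᵢ⁻¹rᵢ and rᵢ is the residual vector of subject i. The Mancl-DeRouen version replaces rᵢ by (I − Hᵢᵢ)⁻¹rᵢ. The t reference has subjects minus 4 degrees of freedom.

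Per-comparison rejection rates:

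| Scenario | Nominal | As planned (ratio) | Sandwich + t | Mancl-DeRouen + normal | Mancl-DeRouen + t |
|---|---|---|---|---|---|
| Interim, 30 per arm | 0.00069 | 0.00157 and 0.00169, two runs (2.3, 2.45) | 0.00117 | 0.00113 | 0.00073 |
| Interim, 27 per arm | 0.00069 | 0.00162 (2.4) | 0.00110 | 0.00104 | 0.00067 |
| Interim, 30, one eye each | 0.00069 | 0.00154 (2.2) | 0.00107 | 0.00098 | 0.00067 |
| Interim, 30, pilot SDs by arm | 0.00069 | 0.00165 (2.4) | 0.00117 | 0.00113 | 0.00073 |
| Interim, 30, heavy-tailed errors (t, 5 df) | 0.00069 | 0.00132 (1.9) | 0.00083 | 0.00081 | 0.00049 |
| Final, 60 per arm | 0.0164 | 0.0194 (1.18) | 0.0183 | 0.0172 | 0.0161 |
| Final, 54 per arm | 0.0164 | 0.0200 (1.22) | 0.0188 | 0.0173 | 0.0162 |
| Final, 54, pilot SDs by arm | 0.0164 | 0.0195 (1.19) | 0.0184 | 0.0169 | 0.0158 |
| Final, 54, heavy-tailed errors | 0.0164 | 0.0192 (1.17) | 0.0180 | 0.0167 | 0.0159 |

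Monte Carlo standard errors are about 0.00004 to 0.00007 at the interim and 0.0004 at the final analysis. Varying the share of two-eyed subjects and the two between-eye correlations gave interim ratios of 2.1 to 2.5. A separate implementation at 27 per arm gave 0.0018 (2.6).

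**Step 4: both looks together** (60,000 trials, 30 then 60 per arm). The rate was 0.0209 per comparison against 0.0167. The chance that any of the three pairs crosses at either look was 0.0548, about 5.5%. With exactly normal statistics it would be about 4.4%, because Bonferroni is conservative for correlated comparisons.

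**Step 5: decision probability at the interim.** Two or more pairs crossed in 0.0002 to 0.0003 of null trials.

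**The case against.** The strongest reply is that the effect is small and partly inferred. Several parts of it stand.

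- The plan is silent on a correction and does not rule one out. That is true, but the normal cut-offs are explicit, and a programmer following the text would produce the uncorrected test.
- Bonferroni slack absorbs much of the inflation: the familywise rate ends only about half a point above 5%. That is true, but the SAP commits to a level per comparison, and that level is missed.
- The planned analysis includes all randomized subjects with multiple imputation, so the number of clusters would be nearer 60 and 30 per arm than 54 and 27. At 60 and 30 the ratios are still about 1.2 and 2.3. Imputation itself was not simulated.
- The pilot changes were more peaked than normal, and heavy-tailed errors lower the interim ratio to 1.9. They leave the final ratio at 1.17.

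A reader might also infer three stronger points, which the documents do not support.

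- One is that the interim test runs at three times its level or more. Runs large enough to estimate so small a probability do not support 3.
- Another is that the interim could wrongly halt the trial or drop an arm at the inflated rate. SAP 3.7.2 makes the boundary non-binding, weighs safety, and considers action only if one arm beats both others or two arms each beat the remaining one. A single crossing triggers nothing.
- The last is that the SAP is wrong to call the cost of monitoring negligible. That statement concerns the alpha spent on the extra look (0.0167 to 0.0164) and is right on its own terms. It makes no claim about small-sample variance.

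**Conclusion.** The rule is wrong as written, by a modest amount and always in the same direction. At the final analysis, which matters most, each comparison runs at about 0.019 to 0.020 against 0.0164, roughly 1.2 times nominal. At the interim the ratio is larger, roughly 2 to 2.6 (about 0.0015 to 0.0018 against 0.0007), but the absolute excess is only about 0.1 percentage point per comparison. Over both looks the familywise rate is about 5.5% against 5%.

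The direction held in every scenario run. The exact ratios rest on the assumed baseline PMD distribution, slope and between-eye baseline correlation, and on complete data.

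**What to change.** In SAP 3.2.2 and 3.7.2 (and Protocol 9.3.1 and 9.8.2), specify the Mancl-DeRouen bias-corrected sandwich with a t reference at both looks. Suitable degrees of freedom are the number of subjects minus the number of model parameters: 90 − 4 = 86 at the interim and 180 − 4 = 176 at the end if all are analysed. Compare the p-values with 0.0007 and 0.0164 in place of comparing Z with 3.394 and 2.400, and state how these degrees of freedom enter the Rubin's-rules pooling.

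Both parts are needed. Either one alone leaves about 0.0010 to 0.0012 at the interim and 0.0172 to 0.0188 at the end in the normal-error runs with equal SDs and 40% two-eyed subjects. The Kauermann-Carroll correction is not an equal substitute: with a t reference it still leaves about 0.0173 to 0.0178 at the final analysis. With heavy-tailed errors the recommended version is slightly conservative at the interim (0.00049).

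The cost is small. A true rate of 0.0200 at a cut-off of 2.400 means that the rule behaves like a cut-off of 2.326, so intervals must widen by 2.400/2.326 = 1.03, about 3%. As a rough guide to power, use one eye per subject, 54 per arm and a 4.5 dB difference: 4.5/(6.5 × √(2/54)) = 3.60. Moving the effective cut-off from 2.326 to 2.400 takes power from Φ(1.27) = 0.90 to Φ(1.20) = 0.88, which is the power that the plan states for that sample size.
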